### 17.3 Populations for Analysis

#### 17.3.1 Enrolled Population

The enrolled population will include subjects who signed informed consent form.

#### 17.3.2 Intent-to-Treat (ITT) Population

The intent-to-treat (ITT) population will include all treated subjects. Analysis based on ITT population will be based on the treatment to which they are treated.

#### 17.3.3 Per Protocol Population (PPP)

The PPP will consist of subjects included in the ITT who are exposed to treatment and have all measurements needed for assessment of the primary endpoint for at least 1 post-baseline visit, and do not have a major protocol deviation.

#### 17.3.4 Protocol Deviations

The following are considered potential protocol deviations:

- No diagnosis of PV.
- Prior therapy does not match with protocol requirements in terms of types of previous therapy regimens.
- No baseline spleen size measurement in the protocol-specified time windows.
- Subjects who take <80% of the prescribed dose over the total duration of study drug dosing as calculated by the Sponsor based on the drug accountability documented by the site staff and monitored by the Sponsor/designee.

Other observations made during the study will also be considered. All potential protocol deviations will be reviewed prior to any interim analysis or database lock. For every potential protocol deviation, a general decision will be made whether to regard it as major or minor, and approved by the Sponsor before database lock. The PPP will be used for efficacy sensitivity analysis.

#### 17.3.5 Safety Population

The Safety Population will include all subjects who have received at least one dose of study drug. For analysis, it will assign subjects to the treatment actually received.

### 17.4 Efficacy Endpoints Analysis

#### 17.4.1 Primary Efficacy Endpoint Analysis

This study will enroll 30 Japanese PV subjects and collect laboratory and clinical data on each subject every 3 months after baseline through 12 months. Primary endpoint analysis will be based on all the evaluable subjects. For each subject at each time point of 3 months, response will be assessed.

The primary efficacy endpoint is the phlebotomy-free complete hematologic responder rate (CHR) at month 9 and month 12.

The phlebotomy-free responder rate is defined as the proportion of patients with complete hematologic response (CHR) and with no phlebotomies during the previous 3 months.

A responder in sense of a primary endpoint is a patient who has met all of the following criteria at month 9 and month 12:

- Hematocrit <45% phlebotomy-free (absence of phlebotomy during the previous 3 months)
- Platelet count  $\leq 400 \times 10^9/L$ ,
- WBC count  $\leq 10 \times 10^9/L$ ,

#### 17.4.2 Secondary Efficacy Endpoints Analyses

The secondary efficacy endpoints are for providing additional supportive evidence of efficacy of the treatment.

- Changes in Hct, WBC, PLT and spleen size from baseline
- Time to requiring no phlebotomy
- Numbers of phlebotomy
- Time to first peripheral blood count response: Cox regression will be performed with treatment, age and baseline factors as the covariates.
- Duration of peripheral blood count response maintenance: Only subjects with response will be included. Mean duration of response will be compared between the two arms using appropriate parametric t-test or non-parametric rank-based test.
- Change from baseline of *JAK2* allelic burden over time: Longitudinal evaluation using repeated measures will be performed.
- Spleen size measurements by sonography will be summarized by scheduled time points, as appropriate.
- Difference in CHR rate between subject with or without of treatment with HU
- Proportion of subjects without thrombotic or hemorrhagic events

Frequencies of disease-related symptoms will be presented in frequency table and compared between treatment arms using chi-square test (or logistic regression with the same factors as used in the primary endpoint analysis).

Additional analyses to those proposed below that may be performed after the completion of the clinical study report (CSR) will be documented in separate reports. These analyses may include but are not limited to the meta-analysis of data from this study combined with data from other studies, or the analysis of biomarkers generated from samples collected during the study but analyzed after database lock and completion of the CSR. In addition, the relationship between biomarker endpoints and safety and efficacy endpoints may be explored. Such data analysis will be described in the SAP.

#### 17.5 Exploratory Analysis

The exploratory analysis consists of bone marrow histological remission. Bone marrow histological remission defined as the disappearance of hypercellularity, trilineage growth (panmyelosis) and absence of >grade 1 reticulin fibrosis (optional).

## 17.6 PPK, E-R, and Immunogenicity Endpoints Analyses

- PPK Analysis
- PK analyses will be performed using the PPK approach and summarized in a separate report where PK parameters, including but not limited to AUC, Cmax, Tmax, and half-life, will be summarized with mean, median, SD, and 95% confidence intervals. The effects of covariates on the PK of P1101 will be investigated.
- E-R Analysis
- The relationship between exposure and key efficacy and safety endpoints will be explored using E-R analysis. The effects of covariates on E-R will be investigated.
- Immunogenicity Analysis
- The proportion of subjects who are positive or negative to anti-P1101 antibody will be summarized.

## 17.7 Safety Endpoints Analysis

Safety data, including ECOG performance status, vital signs, ECGs, heart ECHOs, clinical laboratory tests, physical examinations, lung X-rays, AEs, and ocular examinations, will be summarized by treatment arms and scheduled visits, as appropriate. Change from baseline will be included in summary tables for laboratory, ECG, and vital sign parameters. AEs will be coded by MedDRA and then summarized by system organ class and preferred term for each treatment.

## 17.8 Handling of Missing Data

Missing data will not be imputed, unless otherwise specified. See details in the SAP on the general issue of handling intercurrent events and sensitivity analysis for the primary endpoint.

# 18 ETHICAL AND REGULATORY ASPECTS

## 18.1 Ethics and Good Clinical Practice

This study will be conducted in accordance with the ethical principles laid down in the Declaration of Helsinki. The study protocol and any subsequent amendment(s) will be submitted for approval to an Institutional Review Board (IRB). The study will be conducted in compliance with the protocol, Good Clinical Practice (GCP) regulations and applicable regulatory requirements. The regulatory application or submission for regulatory approval will be made by the Sponsor or its delegate as required by national law.

## 18.2 Institutional Review Board

Before implementing this study, the proposed informed consent, and other information given to subjects must be reviewed by an IRB, and a signed/subscribed and dated statement that the informed consent have been approved by the IRB must be given to Sponsor before study initiation. The IRB membership roster must be provided to the Sponsor. The IRB will review any amendments to the protocol that require formal review and approval. The IRB may be notified for all other amendments (i.e., administrative changes) in accordance with applicable regulatory requirements.

## 18.3 Subject Information and Informed Consent

The Investigator (or a properly trained specialty physician, allocated with this task by the Investigator), should obtain a freely given written consent from each subject after an appropriate explanation of the aims, methods, anticipated benefits, potential hazards and any other aspect of the study that is relevant to the subject's decision to participate. The informed consent form must be signed, with name and date noted by the subject or their legally authorized representative, if applicable, before the subject is exposed to any study-related procedures, including screening tests for eligibility.

The Investigator will explain that the subject is completely free to refuse to enter the study or to withdraw from the study at any time, without any consequences to their current or future care and without the need to justify their decision.

Each subject will be informed that his/her source records may be reviewed by the study monitor, IRB, or a regulatory authority inspector, in accordance with applicable regulations, and that these persons are bound by confidentiality obligations.

#### **18.4 Confidentiality**

The Investigator will ensure that the confidentiality of the subjects' data will be preserved. In the eCRF or any other documents submitted to the Sponsor, the subjects will not be identified by their names, but by an identification system.

The Investigator will maintain documents not meant for submission to the Sponsor, e.g., the confidential subject identification code and the signed informed consent forms, in strict confidence.

Each subject will be informed that a monitor or a regulatory authority inspector, in accordance with applicable regulatory requirements, may review portions of their source records and source data related to the study. Data protection and confidentiality will be handled in compliance with applicable local, regional, and/or international requirements.

### **19 QUALITY CONTROL AND QUALITY ASSURANCE**

#### **19.1 Source Data and Records**

Source data are defined as all the information related to clinical findings, observations, or other activities in the study, added to the original records allowing reconstruction and evaluation of the study.

The Investigator will maintain adequate source records (e.g., files for each enrolled subject). Source records should be preserved for the maximum period of time required by applicable regulations.

All data entered in the eCRF must be supported by source data in the subjects' records.

The Investigator will permit trial-related monitoring, audit(s), IRB review(s), and regulatory inspection(s) by local and/or regional regulatory authorities, as applicable, by providing direct access to source data/records.

The Investigator may authorize site staff (e.g., co-Investigators, nurses) to enter study data into the eCRF.

#### **19.2 Periodic Monitoring**

The monitor will contact and visit the Investigator periodically to review all trial-related source data/records, verify the adherence to the protocol and the completeness, correctness, and accuracy of all eCRF entries compared to source data. The Investigator will cooperate with the monitor to ensure that any discrepancies identified are resolved.

The monitor must be given direct access to source documents (original documents, data, and records). Direct access includes permission to examine, analyze, verify, and reproduce any records and reports that are important to the evaluation of the trial. Source data will be available for all data in the eCRFs, including all laboratory results. Data, which will be continuously monitored during drug administration, will be entered into the eCRF periodically.

#### **19.3 Confidentiality of Subjects' Data**

The Investigator will ensure that the subject's anonymity will be preserved. On eCRFs or any other documents submitted to the Sponsor, the subjects will not be identified by their names, but by a unique subject number. Documents that are not intended for submission to the Sponsor, i.e., the original consent forms and source records, will be maintained by the Investigator in strict confidence and in accordance with regulatory requirements.

## 20 DATA HANDLING AND RECORDKEEPING

### 20.1 Responsibilities of Investigators

The Investigator is accountable for the conduct of the trial at the site. If any responsibilities are delegated, the Investigator should maintain a list of appropriately qualified persons to whom he/she has delegated significant trial-related duties.

### 20.2 Case Report Forms

Electronic Case Report Forms (eCRF) are supplied by the CRO and should be handled in accordance with instructions from the Sponsor. Only the Sponsor approved version of the eCRF should be used for recording study data.

The Investigator is responsible for maintaining adequate and accurate medical records from which accurate information is recorded to eCRFs, which have been designed to record all observations and other data pertinent to the clinical investigation.

eCRFs should be completed by the Investigator or delegate as stated in the site delegation log for all subjects who have signed informed consent.

The Investigator should complete the relevant eCRF pages as soon as possible after each visit observation or clinical laboratory test.

All data sent to the Sponsor must be endorsed by the Investigator.

The Study Monitor should verify the contents against the source data. If the data are unclear or contradictory, queries are sent for corrections or verification of data.

### 20.3 Changes to Case Report Form Data

Errors occurring in eCRFs will be modified by the Investigator or designee, and all changes will be tracked in the audit trail.

### 20.4 Recording, Access, and Retention of Source Data and Study Documents

Source data to be reviewed during this study will include, but is not limited to: subject's medical file, subject ID code list, subject diary cards, original laboratory reports, and histology and pathology reports, investigational medicinal product inventory, 12-lead ECG printouts and echocardiograph reports.

All key data must be recorded in the subject's medical records. Original printouts of data that were generated by technical equipment, for example 12-lead ECG trace, must be labelled with the date that they were printed by the machine, and the subjects' unique identification number. The medical evaluation of such records should be documented as necessary and signed and dated.

The Investigator must permit authorized representatives of the Sponsor, the respective national, local, or foreign regulatory authorities, the IRB, and auditors to inspect facilities and records relevant to this study.

The Study Monitor (and auditors, IRB or regulatory inspectors) may check the CRF entries against the source documents. The consent form includes a statement by which the subject agrees to the monitor/auditor from the Sponsor or its representatives, national or local regulatory authorities or the IRB having access to source data (e.g., subject's medical file, appointment books, original laboratory reports, X-rays etc.).

These records must be made available within reasonable times for inspection and duplication, if required, by a properly authorized representative of any regulatory agency (e.g., the Pharmaceuticals Medical Devices Agency, Japan [PMDA], U.S. Food and Drug Administration [FDA], European Medicines Evaluation Agency [EMEA], UK Medicines and Healthcare products Regulatory Agency [MHRA]) or an auditor.

Essential documents must be maintained according to J-GCP requirements and may not be destroyed without written permission from the Sponsor. The Investigator is required to arrange within the study site, that designated essential documents will be retained for the period as specified in GCP and local regulatory requirements. The head of the study site will designate an archive manager for each type of record to ensure appropriate archiving. The Investigator will be provided with an Investigator Site File at the start of the study. This file contains all relevant documents necessary for the conduct of the study. This file must be safely archived after termination of the study. It is the responsibility of the Investigator or the Head of the Medical Institution to ensure that the subject identification sheets (records stipulated in GCP Ordinance, Article 41 Paragraphs 1 and 2) are stored for at least 15 years (or 2 years after the last Marketing Authorization Application granted for the investigational medicinal product, whichever is longest) beyond the end of the clinical study. All original subject files must be stored for the longest possible time permitted by the regulations at the hospital, research institute, or practice in question. If archiving can no longer be maintained at the site, the Investigator will notify the Sponsor.

## **21 CHANGES IN THE CONDUCT OF THE STUDY**

### **21.1 Protocol Amendments**

Any prospective change to the protocol will be submitted to the IRB and to the competent authority in every country, as required, and should be approved before its implementation.

### **21.2 Premature Study Termination**

Both an Investigator and the Sponsor reserve the right to terminate the study at any time. If this becomes necessary, the procedures will be arranged on an individual study basis after review and consultation by both parties. In terminating the study, the Sponsor and the Investigator will ensure that adequate consideration is given to the protection of the subjects interests. Furthermore, the Investigator should promptly inform the IRB and provide a detailed written explanation that includes the reasons for study termination. The relevant regulatory authorities should be informed according to applicable regulatory requirements.

### **21.3 Publication of Results**

The results of this study may be published or presented at scientific meetings. If this is foreseen, the Investigator agrees to submit all manuscripts or abstracts to the Sponsor prior to submission. This allows the Sponsor to protect proprietary information and to provide comments based on information from other studies that may not yet be available to the Investigator.

In accordance with standard editorial and ethical practice, the Sponsor will generally support publication of multicenter studies only in their entirety and not as individual center data. In this case, a coordinating investigator will be designated by mutual agreement. Any formal publication of the study in which input of the Sponsor's personnel exceeded that of conventional monitoring will be considered as a joint publication by the Investigator and the appropriate Sponsor personnel. In general, the maximum number of authors allowed on any abstract/publication will be used. All screening investigators will be added to the main publication as a group.

## **22 LIABILITIES AND INSURANCE**

In case of any damage or injury occurring to a subject in association with the trial medication or the participation in the study, PharmaEssentia Corporation, will maintain an insurance policy that meets local regulatory requirements. The Investigator is responsible for administering/dispensing the study drug according to this protocol, and for its secure storage and safe handling throughout the study.

## **24 APPENDICES**

## 24.1 Appendix 1. Study Flowchart

	Screening	Treatment phase		End of Treatment	End of Study (Safety follow-up visit)
		every 2 weeks, except visits co-incident to the Assessment visits		Assessment visits - every 12 weeks (month 3, 6 and 9)	Month 12 / Premature discontinuation visit
Informed consent	X				
Inclusion and exclusion criteria	X				
Demographics & medical history	X				
Pregnancy test (urine)	X	X (Every 4 weeks from Week 0)	X	X	X
Heart ECHO standard	X			X	X (cases with early termination only)
12-lead ECG	X	Week 0, Week 0 +96 h Week 2, Week 4, Week 28, Week 28 + 96 h	X	X	X
Physical examination	X	X	X	X	X

Vital signs	X	X	X	X	X
Blood chemistry small panel	X	X	X	X	X
Blood chemistry large panel	X		X	X	
Coagulation (blood)	X		X	X	X
Virology (blood)	X				
Hemoglobin A1c HbA1c)	X				
Hematology small panel	X	X	X	X	X
Hematology large panel	X		X	X	
Immunological parameters (blood)	X		X	X	X
Urine test	X	X	X	X	X
Urine beta 2 microglobulin test	X			X	
ECOG performance status	X	Week 0 only	X	X	X
Spleen size measurement	X	Week 0 only	X	X	
Genetic and mutation test sample (incl. JAK2 allelic burden) (blood)	X	Week 0 only	X	X	
Bone marrow sampling (OPTIONAL)	X			X	
P1101 administration		X	X		
Adverse events	X	X	X	X	X

Concomitant treatment	X	X	X	X	X
Immunogenicity (blood)		Week 0 and Week 4 (Week 0: 0 hr. and 168 hr.) (Week 4: 0 hr.) see Appendix 3	X	X	X
PK (blood)		X (Trough value at every dosing) (4 sampling points per visit at Week 0 and Week 28, see Appendix 2)	X	X	X
HADS	X		X	X	X
Ocular examination	X			X	
Lung X-ray	X			X	

---

Vital signs:	Pulse rate, blood pressure and body temperature.
Blood chemistry small panel:	BUN, ALT, AST, GGT, LDH, total bilirubin.
Blood chemistry large panel:	NT-proBNP or BNP, $\text{Na}^+$ , $\text{K}^+$ , $\text{Ca}^{++}$ , $\text{Cl}^-$ , uric acid, blood glucose, alkaline phosphatase, amylase, lipase, creatinine, total protein, albumin, LDL, HDL, cholesterol, triglycerides, serum iron, transferrin, TSH and fT4.
Coagulation (Blood):	PT-INR, aPTT and fibrinogen.
Virology:	Serology: HBsAg, HCV antibody, HIV antibody
Hematology small panel:	Hemoglobin, hematocrit, platelet count, RBC, WBC.
Hematology large panel:	WBC differential (neutrophils, lymphocytes, monocytes, eosinophils, basophils and reticulocytes), MCV
Immunological parameters:	ANA, TgAb (autoantibodies to thyroglobulin), TPOAb (autoantibodies to thyroid peroxidase).
Urinalysis:	pH, blood, protein, glucose, WBC, nitrite
Spleen size measurement:	ultrasound
Lung X-ray:	For screening, X-rays will be accepted which are not older than 12 weeks prior to the date of screening visit. In case of premature discontinuation, no X-ray examination will be performed (to reduce the burden from exposure to radiation) unless necessary for safety follow-up purposes.

Necessity of Lab examination at Week 0: Week 0 tests can be omitted if the difference in the dates between screening and Week 0 is 7 days or less.

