### **Study Procedures:**

For eligibility purposes, local lab data and local evaluations (incl. mutational status, bone marrow) will be accepted if properly documented in the source data.

Patient visits will be scheduled every 2 weeks: at regular visits, safety and AE data collection with

the basic lab investigations will be performed, while every three months (month 3, 6, 9 and 12) extended assessment visits will be scheduled. A safety follow-up visit will take place 28 days after the end of the last treatment visit.

Study procedures are detailed in the study flowchart (Appendix 1).

Pharmacokinetic (PK) samples will be collected once every 2 weeks at a timing prior to drug administration (at steady state), four consecutively at Week 0 (at first dose) and Week 28 (Appendix 2), at the end of treatment visit, and at the safety follow-up visit.

Assessment of safety will be determined by vital sign measurements, clinical laboratory tests, physical examinations, spleen size measurement by ultrasound, electrocardiogram (ECG) evaluation, lung X-ray, Eastern Cooperative Oncology Group (ECOG) performance status, ophthalmologic investigations, and the incidence and severity of treatment-emergent AEs (TEAEs).

At screening, month 9 and 12, central lab will be testing Hct, WBC and platelets for the purposes of primary endpoint analysis.

Also, a central lab will be in charge of the quantitative allelic burden measurement, as also will perform all further evaluations.

Local labs will be used for other measurement in the study.

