## 9.3 Justification of Inclusion/Exclusion Criteria

### 9.3.1 Justification of Inclusion Criteria

Inclusion criterion 1 was designed to allow for the participation of subjects aged 20 years or older, since this study will be conducted in Japanese adults.

Inclusion criterion 2 identifies the patient population to be enrolled to this study and is based on internationally accepted WHO diagnostic criteria guidelines.

Since the 2016 version was actually widely used after 2017, both the 2008 and 2016 versions are applicable.

Inclusion criterion 3 was established in consultation with the Pharmaceuticals and Medical Devices Agency (PMDA) and considers the group of patients for whom treatment with drug is desired.

In general, the treatment of PV is long-term and is intended for inclusion in young people.

Inclusion criterion 4 was set to include PV patients with a history of treatment with hydroxyurea for no more than 3 years because of concerns about the effect on efficacy and safety in PV patients with a long history of cytoreductive therapy with hydroxyurea and the possibly advanced disease status.

Inclusion criterion 5 is for patients with PV who have not been treated with cytoreductive therapy.

Current national treatment guidelines recommend phlebotomy and aspirin therapy for patients with PV at low risk of thrombosis, but no cytoreductive therapy.

However, foreign NCCN guidelines consider the introduction of cytoreductive therapy in PV patients with low-risk for thrombosis who experiences frequent phlebotomy, worsening of disease-related symptoms, or increased platelets or white blood cell counts. These PV patients are considered "the current standard of treatment is difficult to be applied".

Inclusion criteria 6 and 9 are general criteria for liver function, renal function, and were set to minimize risks in subjects.

Inclusion criteria 7 and 8 were set because they are expected to decrease red blood cell count and neutrophil count due to the cytopenic effects of drug. If these values are low at the time of screening, anaemia and susceptibility to infection are expected to occur. Therefore, these values were set.

Inclusion criterion 10 was set to exclude subjects with psychiatric disorders based on the evaluation of HADS score, since interferon may exacerbate psychiatric disorders.

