### **12.5.2 Dose Reduction and Dose Interruption**

Dose reduction or interruption for P1101 are recommended in subjects experiencing AEs until the AE abates. If intolerance persists after dose reduction or interruption, therapy should be discontinued. These dose changes must be recorded on the Dosage Administration Record and Adverse Event eCRF page.

Dose reduction of the study drugs should be driven exclusively by the safety and tolerability of the drugs under study. If a certain dose is poorly-tolerated and drug-related toxicities arise, the dose has to be reduced to the prior dose, or interrupted, following the scenarios below:

If a subject has a severe (Grade 3 or 4) toxicity, or a drop in absolute neutrophil count (ANC) to below  $0.5 \times 10^9/L$ , temporary interruption has to be implemented until recovery to the condition, which allows treatment continuation (e.g., Grade 1 mild intensity). Treatment re-initiation has to occur from the prior lower dose than those that caused the toxicity. For example, if Grade 3 AE occurs at 500 µg, treatment re-initiation will occur with 450 µg.

If a subject has a Grade 2 toxicity, or a drop in ANC to below  $0.75 \times 10^9/L$  but higher than  $0.5 \times 10^9/L$ , dose decrease without treatment interruption should be considered.

Grade 1 toxicity should not lead to dose reduction or interruption.

Dose re-escalation may be omitted in those subjects who do not recover from previous toxicity.

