## 24.3 Appendix 3. Immunogenecity Sampling

Scheme	Immunogenecity Sample Collection Times Relative to Dosing a							
	Visit 1 (Week 0)	Visit 3 (Week 4)	Visit 7 (Week 12)	Visit 13 (Week 24)	Visit 19 (Week 36)	Visit 27 (Week 52)	EoS (Week 56)	Week 64, 76, 88, and 104 a
	0	0	0	0	0	0	0	0
	168 ( $\pm$ 24)							

aImmunogenicity assessment of anti-P1101 antibodies (anti-drug antibodies; ADA) will be measured at before the first dose (Week 0), 7 days (168 ( $\pm$ 24) hr) after the initial P1101 dose, Week 4, 12, 24, 36, and at End of Treatment (EoT; Week 52), and at the EoS/Follow-up visit (28 days after the final P1101 drug administration at the EoT visit). Blood samples will be collected from the subject confirmed positive for P1101 ADA at EoS visit every three months until ADAs return to baseline levels or up to 12 months.

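### The ANC limits that trigger dose interruption or reduction have no scheduled neutrophil count at 23 of 26 dosing visits, and none after the first dose until Week 12

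*Protocol*

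**What the plan says.** **The dosing rule.** Protocol Section 12.5.2 requires temporary interruption for a Grade 3 or 4 toxicity "or a drop in absolute neutrophil count (ANC) to below" 0.5 x 10^9/L. For an ANC below 0.75 but above 0.5, a decrease without interruption is to be considered.

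**Why neutrophils matter here.** Section 9.3.1 says "Inclusion criteria 7 and 8 were set because they are expected to decrease red blood cell count and neutrophil count" under the drug. Section 5.3 lists leukopenia and neutropenia among drug-related events in more than 10% of subjects in the phase 1/2 dose-escalation study.

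**The laboratory schedule.** Appendix 1 defines two hematology panels:
- Small panel: "Hemoglobin, hematocrit, platelet count, RBC, WBC". It is marked in every column.
- Large panel: "WBC differential (neutrophils, lymphocytes, monocytes, eosinophils, basophils and reticulocytes), MCV". It is marked at screening, at the assessment visits and at Month 12 or premature discontinuation. It is blank in the two-weekly treatment column and at safety follow-up.

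The assessment column is headed "Assessment visits - every 12 weeks (month 3, 6 and 9"), and the ordinary treatment column "every 2 weeks, except visits co-incident to the Assessment visits". The Synopsis agrees: at regular visits "the basic lab investigations will be performed, while every three months (month 3, 6, 9 and 12) extended assessment visits will be scheduled".

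**Text that is less clear.** Table 15-1 lists the differential in one hematology panel with no small/large split. Section 15.3.12 sends the reader to Appendices 1 to 3 for timing. It also says that Visit 1 hematology specimens go to the central laboratory, without saying whether a differential is included.

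**The concern.** A dosing rule needs its input at the visits where it is used. Here the dose is raised every two weeks, but the count that should stop or reverse an increase is scheduled about every 12 to 16 weeks. A site that follows the flowchart exactly will usually not have an ANC when it decides on the next dose.

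Three things are at stake:
- **Dose decisions.** Patients moving from hydroxyurea (HU) receive two cytoreductive drugs together during the Appendix 7 transition, which falls almost wholly before the first on-treatment ANC.
- **The review of higher doses.** Section 12.1 judges tolerability above 300 µg partly by whether a drug-related event required reduction or interruption. ANC is one of the triggers for these.
- **The safety tables.** SAP Section 4.3.1.4 says that unscheduled or repeated assessments done for safety are only listed, apart from those used as baseline. Counts that sites add on their own initiative therefore do not reach the by-visit neutrophil summaries.

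**Working it through.** No sample-size formula applies. The check is a count from the schedule.

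**1. Reproduce the plan's visit numbering.** With visit = week/2 + 1, Weeks 0, 4, 12, 24, 28, 36 and 52 give Visits 1, 3, 7, 13, 15, 19 and 27. These match every visit number in Appendices 2 and 3, including "Visit 27 (Week 52").

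**2. Count dosing visits with a scheduled ANC.** Dosing is two-weekly from Week 0, and the flowchart marks no dose at Month 12.
- Dosing visits, Weeks 0 to 50: 50/2 + 1 = 26.
- With the large panel: Weeks 12, 24 and 36 = 3.
- Without: 26 − 3 = 23.

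Two other readings:
- The Appendix 3 footnote speaks of a final administration at the end-of-treatment visit. Counting Week 52 as a dose gives 27 visits, 4 with the large panel, so 23 of 27 without.
- If the Visit 1 central specimen includes a differential, Week 0 is also covered: 26 − 4 = 22 of 26 without. Sections 15.3.1.1 and 15.4 point away from this, since between them they name only hematocrit, platelets and WBC for the central laboratory.

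Under every reading, no ANC is scheduled after the first dose until Week 12.

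**3. Count escalation steps with a scheduled ANC.** This takes the fastest path in Section 12.5 and, for patients on HU, Appendix 7: +50 µg every two weeks with no hold and no early response.

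| Start | Steps to 500 µg | Weeks of the steps | Before Week 12 | With ANC | Without ANC | Dose at Week 10 |
|---|---|---|---|---|---|---|
| 100 µg | (500 − 100)/50 = 8 | 2 to 16 | 5 | 1 (Week 12) | 7 of 8 | 100 + 5 x 50 = 350 µg |
| 50 µg (HU transition) | (500 − 50)/50 = 9 | 2 to 18 | 5 | 1 (Week 12) | 8 of 9 | 50 + 5 x 50 = 300 µg |

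**4. Day 15 reviews above 300 µg, same path from 100 µg.** The 350 µg dose at Week 10 is reviewed at Week 12, which has a differential. Doses of 400, 450 and 500 µg at Weeks 12, 14 and 16 are reviewed at Weeks 14, 16 and 18, which have none.

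**5. Gaps between scheduled counts.** Screening runs from Day −28 to Day −1, so screening to Week 12 is 12 weeks and 1 day up to 12 + 4 = 16 weeks. Week 36 to Week 52 is 52 − 36 = 16 weeks.

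**6. Can total WBC stand in for ANC?** ANC = WBC x neutrophil fraction, so ANC cannot exceed WBC. A WBC below 0.5 x 10^9/L proves that the interruption limit is crossed. A higher WBC leaves it open, because the fraction is unknown.

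**The case against.** The strongest reply is that the protocol does not stop a site from getting the count. Several parts of it stand.

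- **Unscheduled tests are allowed.** Section 16.2 requires clinically significant abnormal results to be repeated, and the SAP expects unscheduled safety assessments. A reader might infer that the ANC rule cannot be applied at all during escalation. The documents do not support that: Week 12 is itself an escalation visit with a differential, and escalation may run to Week 32 (Section 12.1), so Week 24 can be another.
- **Table 15-1 has one undivided hematology panel.** Some sites may run the differential every time. But Section 15.3.12 gives timing to the appendices, and the Synopsis agrees with the flowchart. The table makes practice dependent on the site; it does not close the gap.
- **Other safeguards exist.** Total WBC is measured every two weeks, laboratory parameters are CTCAE-graded, and safety data are reviewed before each increase above 300 µg. These are partial and do not replace an ANC.
- **Entry is protected.** A reader might infer that the neutrophil floor for entry is unchecked too. It is not: inclusion criterion 8 uses a different limit (1.5 x 10^9/L at screening), and the large panel is marked at screening.
- **Neutropenia is not lost from all safety output.** A clinically significant abnormality that changes dosing is recorded as an adverse event (Section 16.2) and reaches the TEAE tables (SAP Section 4.3.6.1), even if found at an unscheduled test. The loss is in the by-visit laboratory summaries, and the documents do not allow its size to be estimated.

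**Conclusion.** The inconsistency is real and needs correcting: Section 12.5.2 relies on a count that Appendix 1 does not schedule at most of the visits where it is needed. On the flowchart, 23 of 26 dosing visits have no scheduled ANC, with 22 of 26 and 23 of 27 as the alternative readings. At the fastest permitted pace, 7 of 8 increases from 100 µg and 8 of 9 from 50 µg have none.

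The visit counts rest on reading the blank flowchart cell as not scheduled, which the Synopsis and Section 15.3.12 support. The escalation counts also assume uninterrupted two-weekly steps; a hold, an early response or slower escalation would change them. That no count is scheduled between the first dose and Week 12 holds regardless of pace.

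The conclusion is limited to scheduled tests. It does not show that neutropenia would go unnoticed, and it does not touch the primary endpoint, which uses hematocrit, platelets, WBC and phlebotomy. It takes no view on whether the ANC limits or dose rules are right.

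**What to change.** Reconcile Section 12.5.2, Section 15.3.12, Table 15-1 and Appendix 1 so that the laboratory schedule supplies the count on which the dosing rule relies. State in the same change whether the Visit 1 central specimen includes a differential.

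One way is to report the WBC differential from the local blood count already drawn with the small panel. Scheduled ANC would then cover 26 of 26 dosing visits instead of 3, and 8 of 8 escalation steps from 100 µg (9 of 9 from 50 µg) instead of 1. Where Week 0 tests are omitted because screening was 7 days or less before, the screening large panel already holds the count. The by-visit neutrophil summaries would fill from scheduled values, with no change to the SAP rule on unscheduled tests.

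Leave all ANC limits and dose rules unchanged. The change is an edit to the panel definitions with matching text in Table 15-1, plus a local laboratory order. The downside is the added cost of the differential; the documents give no figure, but it should be small because the blood is already drawn at these visits.
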